# Modification

## Basic Info

Confirmation Number:	dbjiagia
Protocol Number:	825000
Created By:	[name]
Principal Investigator:	[name]
Protocol Title:	The Role of Palliative Care Interventions to Reduce Circadian Rhythm Disorders in Persons with Dementia Healthy Patterns Study
Short Title:	Healthy Patterns Sleep Study
Protocol Description:	This Phase III efficacy trial of the Healthy Patterns intervention, a home-based activity intervention, is designed to improve symptoms of circadian rhythm disorders (CRD) and quality of life (QOL) in home dwelling person with dementia. We will use a randomized two-group parallel design of 200 people with dementia and their caregivers assigned to intervention or attention control intervention. Outcomes include measures of QOL as well as actigraphic and proxy reported measures of CRDs
Submission Type:	Social and Biological Sciences
Application Type:	EXPEDITED Category 7 and Category 3

## PennERA Protocol Status

Approved

### Resubmission\*

No

### Are you submitting a Modification to this protocol?\*

Yes

## Current Status of Study

### Study Status

Currently in Progress

*If study is currently in progress, please enter the following*

### Number of subjects enrolled at Penn since the study was initiated

170

### Actual enrollment at participating centers

170

*If study is closed to further enrollment, please enter the following*

### Number of subjects in therapy or intervention

0

**Number of subjects in long-term follow-up only**

35

**IRB Determination**

If the change represents more than minimal risk to subjects, it must be reviewed and approved by the IRB at a convened meeting. For a modification to be considered more than minimal risk, the proposed change would increase the risk of discomfort or decrease benefit. The IRB must review and approve the proposed change at a convened meeting before the change can be implemented unless the change is necessary to eliminate an immediate hazard to the research participants. In the case of a change implemented to eliminate an immediate hazard to participants, the IRB will review the change to determine that it is consistent with ensuring the participant's continued welfare. Examples: Convened Board Increase in target enrollment for investigator initiated research or potential Phase I research Expanding inclusion or removing exclusion criteria where the new population may be at increased risk Revised risk information with active participants Minor risk revisions that may affect a subject's willingness to continue to participate Expedited Review Increase in target enrollment at Penn where overall enrollment target is not exceeded or potentially sponsored research Expanding inclusion or removing exclusion where the new population has the same expected risk as the previous, based on similarities of condition Revised risk information with subjects in long-term follow-up Minor risk revisions with no subjects enrolled to date

Expedited Review

**Modification Summary**

Please describe any required modification to the protocol. If you are using this form to submit an exception or report a deviation, enter 'N/A' in the box below.

We are adding a questionnaire to our three-month follow-up calls with our participants. This questionnaire is called the University of Pittsburgh COVID Caregiving Questionnaire and is attached. It seeks to ask persons with dementia and their caregivers about their experiences with the COVID-19 pandemic. We are also hoping to make the following personnel changes. Removing Personnel Remove [name] as Study Contact Adding Personnel Add [name] as Study Contact o Department: 602, Biobehavioral Health Sciences o Role: Research Project Manager o Email: [contact] o Address: [name] Add [name] as Key Study Personnel o Department: School of Nursing o Role: Research Assistant o Email: [contact] Add [name] as Key Study Personnel o Department: School of Nursing o Role: Research Assistant o Email: [contact]

**Risk / Benefit**

Does this amendment alter the Risk/Benefit profile of the study?

No

**Change in Consent**

Has there been a change in the consent documents?

No

**If YES, please choose from the options below regarding re-consenting**

## Deviations

**Are you reporting a deviation to this protocol?\***

No

## Exceptions

Are you reporting an exception to this protocol?\*

No

# Protocol Details

## Resubmission\*

Yes

## Hospital Sites

Will any research activities and/or services be conducted at a Penn Medicine affiliated hospital site?

No

#### **Responsible Org (Department/School/Division):**

600 - School of Nursing

#### **Disclosure of Significant Financial Interests\***

Does any person who is responsible for the design, conduct, or reporting of this research protocol have a **FINANCIAL INTEREST**?

No

#### **Penn Intellectual Property\***

To the best of the Principal Investigator's knowledge, does this protocol involve the testing, development or evaluation of a drug, device, product, or other type of intellectual property (IP) that is owned by or assigned to the University of Pennsylvania?

No

#### **Certification**

I have reviewed the *Financial Disclosure and Presumptively Prohibited Conflicts for Faculty Participating in Clinical Trials* and the *Financial Disclosure Policy for Research and Sponsored Projects* with all persons who are responsible for the design, conduct, or reporting of this research; and all required Disclosures have been attached to this application.

Yes

# Social and Biological Sciences

## Study Instruments

Discuss the particulars of the research instruments, questionnaires and other evaluation instruments in detail. Provide validation documentation and or procedures to be used to validate instruments. For well known and generally accepted test instruments the detail here can be brief. More detail may be required for a novel or new instrument. For ethnographic studies identify any study instruments to be used (i.e. for deception studies) and describe in detail where, when and how the study will be conducted and who or what are the subjects of study. Note: For more information on how to conduct ethical and valid ethnographic research, follow the link For oral histories or interviews provide the general framework for questioning and means of data collection. If interviews or groups settings are to be audio taped or video taped describe in detail the conditions under which it will take place. Include a copy of any novel or new test instruments with the IRB submission.

All measures to be used in the study are established indexes. No new or novel instruments will be used. Quality of life in persons with dementia will be assessed using two well established measures the QOL-AD and the PHQ-9. The dementia-specific 13-item Quality of Life in Alzheimer's Disease scale reflects multiple dimensions (physical, social, emotional, and functional well-being) with each rated as 1=poor, 2=fair, 3=good, or 4=excellent. A total score representing the sum of items ranging from 13 to 52 will be derived separately for persons with dementia and the family caregivers (CG). In addition, CG will be asked to complete the PHQ-9. Persons with dementia will be administered the MMSE. Other instruments include the MMSE, the Barthel Index, Cognitive status will be measured at baseline using the Mini Mental State Exam (MMSE) Physical function will be measured at baseline using the Barthel Index. Neuropsychiatric symptoms will be measured using the Neuropsychiatric Inventory (NPI) Sleep disturbance will be assessed using the PROMIS Sleep Related Impairment index. Neuroendocrine activity in persons with dementia will be assessed using the biological signature of the HPA response via salivary cortisol. CG will be instructed to collect assays at the awakening challenge and at 3 additional intervals (30 minutes after waking, mid day, and at bedtime one hour after dim light exposure). Caregivers will be provided all materials and marked plastic bags to freeze samples until pick up by the trained data collector. Caregivers will be asked to collect saliva for 2 consecutive days prior to the first study visit, and again after the last intervention visit. Sleep-wake activity will be measured using an actigraphy bracelet worn by the person with dementia. The Motionlogger actigraph, which is manufactured by AMI and utilize the same algorithm as used in earlier studies of community dwelling persons with dementia, will be placed on the non-dominant wrist at baseline and will be worn for consecutive 24 h-periods until removal at 1 month (T2) data collection. Actigraphs will be set to collect data in 60-second epochs via tri directional accelerometer using a validated algorhythm. The primary measure of interest will be number of minutes of wake after sleep onset (WASO). Other parameters that will also be subject to analysis include total sleep time (TST), day/night sleep ratio, and number of night awakening. There will NOT be any remote monitoring or data transfer with the actigraph through a wireless connection.

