## Method for Assigning Subjects to Groups

Describe how subjects will be randomized to groups.

After completing all baseline measurement subjects will be randomly assigned to intervention or control conditions. The project manager will prepare sealed envelopes and enact randomization. These envelopes will indicate on the outside the sequential recruitment number. Inside will be the subjects group assignment, determined using a random number generator. The project manager will open the envelopes and contact respective interventionists within 48 hours of randomization. Maintaining blindness to group assignment is assured at baseline since randomization occurs only after completion of that visit. Randomization procedures will be the responsibility of the project manager, who will not disclose subject assignment to data collectors.

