Once eligibility is determined and consent is signed, dyads of persons with dementia and their caregivers will receive a baseline home interview (T1). Following the baseline interview, participants will be randomly assigned to experimental or attention-control group conditions. Experimental dyads will receive up to 8 contacts with a interventionist over 1-month. The attention-control group dyads will receive comparable attention in a structured program involving the same number and mix of in-home and telephone contact as the treatment group. All dyads will be retested at 1-month from baseline (T2) to evaluate proximal outcomes of neuropsychiatric symptoms, QOL, and sleep quality and at 4 months (T3) to evaluate sustained uptake and distal outcomes of QOL and other measures of satisfaction with the study procedures. Outcome measures will be assessed by interviewers masked to treatment assignment. In addition, participants will be asked about their experience with the COVID-19 pandemic (using the University of Pittsburgh COVID Caregiving Questionnaire) at T3. This data will be collected via telephone only. The only information collected will include their answers to the questions on the survey and their de-identified participant number.

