**Procedures**

The proposed study is a prospective, single blind, two group randomized trial to test whether a timed activity intervention improves symptoms of CRD compared to an attention control condition and to investigate the mechanisms by which CRDs are influenced by a timed activity intervention. Interested CGs who contact the research team will be screened for eligibility by telephone. Those initially eligible and willing, will receive a clinician assessment to obtain written informed consent and to rule out primary sleep disorders requiring specialty care. Once eligibility is determined dyads will receive a baseline home interview (T1). Following the baseline interview, participants will be randomly assigned to experimental or attention-control group conditions and will be contacted to be informed of their respective group assignment within 48 hours of randomization. Experimental dyads will receive up to 8 contacts with a trained nurse interventionist over 1-month. The attention-control group dyads will receive comparable attention in a structured program involving the same number and mix of in-home and telephone contact as the treatment group. All dyads will be retested at 1-month from baseline (T2) to evaluate proximal outcomes of CRD symptoms, QoL, and CG sleep quality; and at 4 months to evaluate distal outcomes including QoL and other measures of satisfaction with the study procedures. Outcome measures will be assessed by interviewers masked to treatment assignment. Timed Activity Intervention Protocol: The timed activity group will involve 4 in-home visits in the mid morning and up to 4 brief telephone education sessions in the evening provided over 4 weeks. The timed activity intervention provides activities delivered at specific times in the daily cycle; it is theory-based, its components have been tested in pilot work; and it is portable and replicable (e.g., protocols are manualized). As in the pilot studies, the in-home sessions are spaced weekly so that the participants can have the opportunity to practice the activity with the interventionist and then on their own. During each session the interventionist will reinforce activity use, review problem solving approaches and provide education. In Session 1 (home visit), the interventionist will explain the nature of the visit and assess the health and functional status and preferences/interests of the PwAD. The interventionist will then provide a suggested morning activity that will match the functional capabilities and interests of the PwAD i.e., based on repetitive motion (e.g., folding towels; sorting objects) and integrating multi-sensory stimulation (photos of interest, objects pleasant to touch). Activities selected are simplified (1 to 2 steps vs. multiple, complex steps), to minimize errors. In Session 2 a follow up phone call will be provided on the following evening to provide coaching in the morning activity. In Session 3 (home visit) the interventionist will review the implementation of morning activities and provide training materials for the evening relaxation protocol. The evening relaxation protocol is a brief 10-step reflexology intervention in which pressure is applied to each of the reflex points on the feet for 30 seconds at a time for a total of 10 minutes. The protocol sequence is based on best practice guidelines. CG are provided a flip book and a CD-ROM demonstrating the procedure and developed in our pilot stud. In Sessions 4-5 (one home visit and one phone call), the interventionist will review integration of

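### Does the actigraphy schedule let the intervention leak into the baseline WASO value?

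*Combined protocol and SAP*

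**What the plan says.** - Study Instruments: the device "will be placed on the non-dominant wrist at baseline and will be worn for consecutive 24 h-periods until removal at 1 month (T2". WASO is named there as the main actigraphy measure.
- Study Instruments, on cortisol: "Caregivers will be asked to collect saliva for 2 consecutive days prior to the first study visit, and again after the last intervention visit".
- Method for Assigning Subjects to Groups: "After completing all baseline measurement subjects will be randomly assigned to intervention or control conditions". The same paragraph, on blinding, adds that "randomization occurs only after completion of that visit".
- Administration of Surveys and/or Process: "Following the baseline interview, participants will be randomly assigned to experimental or attention-control group conditions".
- Procedures: dyads "will be contacted to be informed of their respective group assignment within 48 hours of randomization"; "the in-home sessions are spaced weekly"; and "In Session 3 (home visit) the interventionist will review the implementation of morning activities and provide training materials for the evening relaxation protocol".
- Analysis Plan, Aim 1: the T2-T1 difference is compared between groups with T1 as a covariate. Aim 3 reuses the baseline-adjusted change.
- Procedures also refers to an uploaded Table 1 of variables and testing occasions. It is not in the text available for review, so what it contains cannot be counted as missing.

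**The concern.** A device first put on at the baseline visit has recorded no night when that visit ends. If randomization followed at once and notice came within 48 hours, some or all T1 nights could fall after assignment, and perhaps after Session 1. T1 and T2 are cut from one continuous recording, and the text gives no cut point. Subject Privacy describes consent and baseline as one home visit, which appears to leave no earlier occasion to place the device.

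At stake is the T1-adjusted effect on WASO and the other actigraphy measures, plus the Aim 3 mediation models. If T1 already carried part of the benefit, subtracting it and adjusting for it would remove part of the effect being estimated. Interview measures such as the Neuropsychiatric Inventory, which covers the other listed primary outcome, do not depend on device nights.

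**Working it through.** **1. Sequence.** The assignment rule puts all baseline measurement before randomization, and the Analysis Plan calls T1 the baseline observation. Read literally, T1 WASO is complete before randomization. The blinding sentence ties randomization to the end of the visit but sets no interval after it. The 48 hours run from randomization, not from device placement. Procedures has a clinician assessment with consent before the baseline interview, so the one-visit reading is not the only one. The two-day saliva collection also fits a baseline that spans several days.

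**2. Slack before T2.** Four weekly home visits span 3 × 7 = 21 days. With T2 at 28 to 31 days (assumed meaning of one month), 7 to 10 days remain, or 5 to 8 if two saliva days follow the last visit. Part or all of this may fall before Session 1. No day for Session 1 is given.

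**3. The plan's own figure.** n = 2(1.960 + 0.842)²/0.45² = 77.5, so 78 per group; 78/(1 − 0.22) = 100. Both are reproduced. Noncentral-t power at 78 per group is 79.75%.

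**4. Size of the possible bias.** Let f be the share of the final effect already present in the T1 nights and b the slope of T2 on T1. Neither is in the documents. The expected estimate is d(1 − fb).

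Assume a linear build-up from night 1 to night 28, so the effect on night k is (k − 1)/27. The mean over nights 1 to 7 is 3/27 and over nights 22 to 28 is 24/27, giving f = 3/24 = 0.125. A later start gives f = 0.065 (after night 3) or 0 (after night 7). At f = 0.125, two-sided alpha 0.05 and 78 per group:

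| Scale of d = 0.45 | b | Clean T1 | Exposed 7-night T1 |
|---|---|---|---|
| Adjusted | 0.5 | 79.75% | d = 0.422, 74.5% |
| Adjusted | 0.7 | 79.75% | d = 0.411, 72.2% |
| Raw, divided by √(1 − b²) | 0.5 | 89.7% | 85.6% |
| Raw, divided by √(1 − b²) | 0.7 | 97.4% | 94.6% |

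With no true effect there is nothing to leak into T1, so false positives are not inflated by this route.

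**5. Would a strict rule help?** In this scenario night 2 already carries 1/27 of the effect, so only night 1 is clean. A one-night T1 has slope b√(rel₁/rel₇), where rel_k = k·ICC/(1 + (k − 1)·ICC) is the reliability of a k-night mean and ICC is the assumed single-night value. For ICC 0.3, rel₁ = 0.30 and rel₇ = 0.75. At b = 0.5 the slope is 0.316, the effective d is 0.45/√(1 − 0.1) = 0.474, and power is 83.7%. All cells, raw scale, 78 per group:

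| b | ICC 0.3 | ICC 0.5 | ICC 0.7 | Exposed 7-night T1 |
|---|---|---|---|---|
| 0.5 | 83.7% | 85.5% | 87.2% | 85.6% |
| 0.7 | 87.6% | 90.8% | 93.8% | 94.6% |

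The clean one-night T1 removes the bias but has lower power in five of six cells, one of them a near tie (85.5% against 85.6%).

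**The case for a change.** The best case for a change is that WASO is the primary sleep measure, its T1 value enters the analysis twice, and the nights that define it are not written down in the available text, so the window could be chosen after the data exist. Writing it down needs no new data. The linear build-up may also be too kind. At f = 0.3 and b = 0.5 power is 66.1% on the adjusted scale or 78.3% on the raw scale. If the full effect arrived at once, a 7-night window with Session 1 on day 3 would give f = 5/7 = 0.71.

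Two parts of this stand: the window is not stated in the visible text, and placement at baseline is not expressly reconciled with the rule that all baseline measurement comes first. The harm is not shown. It needs a T1 window that overruns Session 1, against the assignment rule, and an intervention that changes sleep within days. The session content makes an immediate full effect unlikely: Session 1 offers a morning activity, evening relaxation training starts at Session 3, and written environmental cues for sleep come at Sessions 4-5. The larger losses therefore describe an analyst departing from the plan's stated order under a fast-acting effect.

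**Conclusion.** No change is needed. This is a missing detail that an analyst following the assignment rule, or simply taking T1 nights before Session 1, would fill soundly. The bias is then zero and power stays at 79.75% for 78 per group. In the illustrated 7-night case, with onset after night 1, the loss is 4.1 to 5.3 percentage points at b = 0.5 and 2.8 to 7.6 at b = 0.7, always towards the null. These figures rest on assumed values of f, b, the build-up and the ICC. They illustrate the size and do not bound it. Forcing a very short clean T1 trades that bias for a noisier covariate and often costs as much power as it saves. The Neuropsychiatric Inventory outcome and the sample size of 200 dyads are untouched.

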
## Group Modifications

Describe necessary changes that will or have been made to the study instruments for different groups.

None

## Method for Assigning Subjects to Groups

Describe how subjects will be randomized to groups.

After completing all baseline measurement subjects will be randomly assigned to intervention or control conditions. The project manager will prepare sealed envelopes and enact randomization. These envelopes will indicate on the outside the sequential recruitment number. Inside will be the subjects group assignment, determined using a random number generator. The project manager will open the envelopes and contact respective interventionists within 48 hours of randomization. Maintaining blindness to group assignment is assured at baseline since randomization occurs only after completion of that visit. Randomization procedures will be the responsibility of the project manager, who will not disclose subject assignment to data collectors.

## Administration of Surveys and/or Process

Describe the approximate time and frequency for administering surveys and/or evaluations. For surveys, questionnaires and evaluations presented to groups and in settings such as high schools, focus group sessions or community treatment centers explain how the process will be administered and who will oversee the process. For instance, discuss the potential issues of having teachers and other school

personnel administer instruments to minors who are students especially if the content is sensitive in nature. Describe the procedure for audio and videotaping individual interviews and/or focus groups and the storage of the tapes. For instance, if audio tape recording is to be used in a classroom setting, describe how this will be managed if individuals in the class are not participating in the study. Explain if the research involves the review of records (including public databases or registries) with identifiable private information. If so, describe the type of information gathered from the records and if identifiers will be collected and retained with the data after it is retrieved. Describe the kinds of identifiers to be obtained, (i.e. names, social security numbers) and how long the identifiers will be retained and justification for use.

Once eligibility is determined and consent is signed, dyads of persons with dementia and their caregivers will receive a baseline home interview (T1). Following the baseline interview, participants will be randomly assigned to experimental or attention-control group conditions. Experimental dyads will receive up to 8 contacts with a interventionist over 1-month. The attention-control group dyads will receive comparable attention in a structured program involving the same number and mix of in-home and telephone contact as the treatment group. All dyads will be retested at 1-month from baseline (T2) to evaluate proximal outcomes of neuropsychiatric symptoms, QOL, and sleep quality and at 4 months (T3) to evaluate sustained uptake and distal outcomes of QOL and other measures of satisfaction with the study procedures. Outcome measures will be assessed by interviewers masked to treatment assignment. In addition, participants will be asked about their experience with the COVID-19 pandemic (using the University of Pittsburgh COVID Caregiving Questionnaire) at T3. This data will be collected via telephone only. The only information collected will include their answers to the questions on the survey and their de-identified participant number.

